Quasi-Randomized Evaluation of the UCLA Next Day Clinic (NDC)

NCT ID: 24-000913

Updated 08/15/2024

Statistical analysis. For the primary analysis, we will compare DAOH between eligible patients in the treatment and control arms as-randomized using an instrumental variable (IV) analysis, with encouragement to refer (even/odd birth date) as the binary instrumental variable and treatment setting (NDC v. inpatient) as the exposure. Analysis will utilize a two-stage least squares approach. In the first stage, we will regress treatment setting on the instrument and all covariates. In the second stage, we will use predicted values of treatment setting to estimate differences in DAOH between arms, adjusting for the same covariates. This procedure will be repeated for the secondary outcomes of global health-related quality of life, patient experience, and the financial analysis. Covariates will include: diagnosis, comorbidity score, age, sex, insurance type, zip code, and race/ ethnicity. We will use heteroskedasticity-robust standard errors. We will evaluate the NDC's impact on health disparities by performing subgroup analyses across racial/ethnic, sex, age, and socioeconomic lines, ensuring outcomes do not differ and that all groups have equitable access to the NDC.

We will perform the following three secondary analyses:

- 1) Subset analysis to define a specific subgroup of patients based on the probability of being referred to the NDC. Specifically, we will use a logistic regression based on patient labs, vitals, characteristics, and comorbidities to estimate the probability of referral to NDC, and use a median split to define a threshold. We will then apply this threshold to the control group, and repeat the primary analysis of treatment v. control group only including patients above the pre-specified threshold.
- 2) Per-protocol analysis of eligible patients repeating the primary analysis methodology but only among patients who adhered to the assignment and treatment protocol.

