- 3) Difference-in-differences (DiD) analysis using UCLA Santa Monica Medical Center as a control. We will compare 30-day DAOH among the eligible cohort at Ronald Reagan UCLA Medical Center to a matched eligible cohort at UCLA Santa Monica Medical Center (cohorts will be constructed using the same logic and rules). The dependent variable will be 30-day DAOH, the independent variables will be hospital location, intervention period, location x intervention interaction, and the above specified covariates.

We will also perform a formal cost-effectiveness analysis (CEA) using standard CEA methodologies to measure the incremental cost-effectiveness ratio (ICER).

For the patient-reported secondary outcomes, we will perform a complete case analysis as the primary analysis, but as a sensitivity analysis we will estimate the probability of responding to the survey using a logistic regression model informed by baseline patient characteristics, and do an inverse probability-weighted analysis to correct for non-response.

Sample size and power. Based on historical UCLA data, we expect 850 patients to be randomized in a 12-month period. Assuming similar numbers during this trial, a 1:1 randomization by birthdate would trigger the encouragement 425 times. On an as-randomized basis, two groups of 425 patients would provide 80% power to detect an effect size as small as 0.192 standard deviations (SDs) on our primary outcome, DAOH, assuming a two-sample t-test and a two-sided 0.05 significance level. If ED physicians and patients accept the 425

encouragements 50% of the time in the treatment group and there is 10% contamination in the control group (i.e., 10% of eligible patients randomized to control get referred to the NDC), then the delta effect of the instrument on referral will be 40%. Thus, the IV parameter will be $0.192 / 0.40 = 0.48$ SDs. In the historical sample, mean DAOH was 26.8 with a SD of 2.2 days. We will therefore have 80% power to detect an IV effect of referral to the NDC of $2.2 * 0.48 = 1.1$ days.

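### Secondary analysis 1 does not say where the referral model is fitted; if it is the treatment arm, scored in-sample, the subset's two arms are selected differently and the IV estimate can be biased

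*SAP*

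**What the plan says.** The first of the three secondary analyses in the SAP (Statistical analysis) restricts the comparison to patients likely to be referred. For this, "we will use a logistic regression based on patient labs, vitals, characteristics, and comorbidities to estimate the probability of referral to NDC", and the plan will then "use a median split to define a threshold". The next step is: "We will then apply this threshold to the control group, and repeat the primary analysis of treatment v. control group only including patients above the" cut; the sentence closes with "only including patients above the pre-specified threshold". The repeated analysis is the instrumental-variable comparison with birth-date parity as instrument ("Analysis will utilize a two-stage least squares approach").

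The SAP does not state the sample in which the model is fitted, the sample whose median is taken, the number of predictors, or any hold-out, cross-fitting or external data. It gives no coefficients and no cut-off value.

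**The concern.** A cut that is afterwards carried over to controls was evidently derived elsewhere. The treatment arm is the natural source, because the plan expects 50% referral there and 10% among controls. On that reading, a treatment patient's own referral helps decide whether that patient enters the subset, while a control's referral plays no part in the control's selection.

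A model with many predictors and few referrals absorbs chance. It pulls referred treatment patients above the cut and pushes non-referred ones below it. Selection then depends on a post-assignment event in one arm only. Two things follow:

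- The referral share among selected treatment patients looks higher than it would in new patients with the same scores.
- Within the subset, birth-date parity is no longer exactly independent of whatever drove referral beyond the recorded predictors. If that driver also bears on DAOH, 2SLS does not remove the resulting difference, because the imbalance runs along the instrument itself.

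**Working it through.** **Inputs from the SAP (Sample size and power).** 425 per arm, referral 50% v. 10%, DAOH mean 26.8 and SD 2.2 days, two-sided 0.05. Expected referrals available for fitting: 0.50 × 425 ≈ 212.

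**1. The plan's own figure.** (1.960 + 0.842) × √(2/425) = 0.192 SD, and power at 0.192 SD is 79.9%. Then 0.192/0.40 = 0.48 SD, and 2.2 × 0.48 = 1.06, given as 1.1 days. The figure reproduces. It is for the whole cohort; the SAP gives none for the subset.

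**2. Scale in the subset.** About 212 per arm lie above the median. The detectable difference is 2.802 × √(2/212) = 0.272 SD, so 2.2 × 0.272/0.40 = 1.50 days at an unchanged 40% first stage. With the simulated first stage of about 0.52 (20 predictors, in-sample), the standard error is about 2.2 × √(2/212)/0.52 = 0.41 days.

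**3. Plausible model size.** The SAP's eligibility list has seven labs and vitals and 15 diagnosis groups. If diagnosis counts as a patient characteristic, 7 + 14 + age + sex = 23 parameters, before insurance, race/ethnicity, comorbidities or zip code. Without diagnosis, 15 to 20 is reasonable. The SAP gives no count, so k is an assumption.

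**4. Simulation with no true NDC effect.** Assumed: k standard normal predictors, of which five are informative; one unrecorded standard normal driver of referral, correlated ρ with DAOH; DAOH normal. The logistic model is fitted in the treatment arm, its median is applied to both arms, and 2SLS is adjusted for the predictors with robust standard errors. There were 1,000 replicates per setting (Monte Carlo SE 0.013 to 0.014 days).

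| k | Arm gap in unrecorded driver (SD, ρ = 0.3) | Bias, ρ = 0.3 (days) | Type I error | Bias, ρ = 0.5 (days) | Type I error |
|---|---|---|---|---|---|
| 10 | 0.034 | +0.046 | 4.1% | +0.065 | 6.6% |
| 20 | 0.074 | +0.050 | 6.1% | +0.121 | 6.2% |
| 40 | 0.132 | +0.175 | 10.5% | +0.272 | 14.7% |
| 60 | 0.185 | +0.204 | 12.0% | +0.345 | 20.0% |

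**5. Hand check.** Bias ≈ 2.2 × ρ × gap / first stage. For k = 40, ρ = 0.3: 2.2 × 0.3 × 0.132/(0.697 − 0.148) = 0.16 days, against 0.175 simulated. For k = 20, ρ = 0.3: 2.2 × 0.3 × 0.074/(0.675 − 0.153) = 0.09, against 0.050 here and 0.075 to 0.095 in separate runs of 600. The 20-predictor figure is therefore known only to about 0.05 to 0.10 days.

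**6. Sign.** In adjusted runs of 600 replicates with ρ = 0, the mean was +0.013, −0.019 and −0.005 days at k = 10, 20 and 40, which is no bias. With ρ = −0.3 it was −0.030, −0.118 and −0.163 days, against the NDC.

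**7. Other ways of scoring (k = 20, ρ = 0.3, adjusted; 300 replicates for cross-fitting, 600 for the others).**

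| Scoring | Referral share, selected treatment patients | Arm gap (SD) | Bias (days) | Type I error |
|---|---|---|---|---|
| In-sample | 67.5% | +0.074 | +0.095 | 5.5% |
| 10-fold cross-fitted | 62.4% | −0.006 | −0.030 | 5.3% |
| External model | 62.6% | −0.003 | 0.000 | 5.2% |
| Both arms pooled | 65.8% | +0.030 | +0.010 | 4.7% |

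The in-sample share is overstated by 67.5 − 62.4 = 5.1 points. Unadjusted cross-fitted and external runs gave −0.003 and +0.048 days. With so few replicates, the arm gap is the cleaner evidence that the asymmetry is removed.

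**8. Other simulators.** These gave the unrecorded driver log-odds of 1 per SD of referral and ρ of 0.3 to 0.5. False gains were 0.02 to 0.09 days at 15 to 25 predictors and 0.06 to 0.19 at 40 to 60, with type I error up to about 9%. A version built on the SAP's own lists (31 or 40 parameters) gave 0.07 to 0.14 days, type I error 5% to 7%, and a referral share of 69% v. about 61% cross-fitted. One simulation at 60 predictors gave 70% v. 56%. Cross-fitted means were mostly near zero; one simulator ranged from −0.08 to 0.00 days.

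**The case against.** Four points can fairly be made against the concern.

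- **The fitting sample is inferred.** The SAP carries a threshold over to controls; it does not say that controls were left out of the fit. Calling the threshold pre-specified would suit a cut fixed beforehand from outside data, in which case the problem disappears. Pooled fitting roughly halves the arm gap. This stands, and it is why the first remedy is to name the sample. The label alone does not settle the matter, since no value, coefficients or data source accompany it.
- **The direction is not given.** A reader might infer that the subset, as written, overstates the NDC effect. The documents do not support that. The sign follows the relation between unrecorded reasons for referral and DAOH, on which the SAP is silent. That physicians divert healthier-looking patients is plausible, but it remains an assumption.
- **The size is modest.** At 15 to 25 predictors the bias is roughly a quarter of the subset standard error or less, and type I error is near nominal. The larger figures need 40 to 60 parameters, and the simulators differ on them. This stands. A reader might also infer that the instrument is broken outright; a gap of 0.03 to 0.18 SD is a loss of exact balance and does not justify that description.
- **The reach is limited.** Only one of three secondary analyses is touched. The primary 2SLS and the calculation behind "two groups of 425 patients would provide 80% power to detect an effect size as small as 0.192 standard deviations" are unaffected.

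What survives is that nothing in the SAP prevents the asymmetric selection, and that the inflated referral share does not depend on any prognostic link.

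**Conclusion.** The concern holds in a conditional form. If the model is fitted in the treatment arm and those patients are scored in-sample, the arms of the subset are selected by different rules. The referral share among selected treatment patients is then overstated by about 4 to 12 points over 15 to 60 assumed predictors (14 in one simulation at 60).

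The IV estimate is biased only if unrecorded drivers of referral relate to DAOH: toward the NDC if healthier patients are referred, away from it if the reverse. With assumed correlations of 0.3 to 0.5, the bias is under about 0.1 days at 15 to 25 predictors (0.12 at the upper end) and about 0.06 to 0.35 days at 40 to 60. Type I error departs clearly from 5% only with large models, where the highest simulated value is 20%.

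These sizes rest on the assumed predictor count, the assumed correlation and normally distributed DAOH, none of which the SAP supplies. Priority is low to moderate.

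**What to change.** In secondary analysis 1:

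- State that the referral model is fitted in the treatment arm, and list its predictors.
- Score each treatment patient by 10-fold cross-fitting, so that no patient is scored by a model that used that patient's referral.
- Score controls with the full treatment-arm model or the average of the fold models.
- Take one median cut from the out-of-sample scores and apply it to both arms.
- Drop the description of the threshold as pre-specified, or justify it with a value and a source.

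Alternatively, fix both model and cut from pre-trial referral data, if such data exist.

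The cost is a sentence or two in the SAP and a few lines of code. The apparent referral rate in the subset will be slightly lower and the interval wider: at 20 predictors the first stage falls from 0.675 − 0.153 = 0.52 to 0.624 − 0.155 = 0.47, which widens the interval by about 0.52/0.47 = 1.11, or 11%.

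### The per-protocol analysis repeats the instrumental-variable method among adherers, where, on the natural reading, instrument and exposure coincide and the method becomes ordinary regression in a sample selected after assignment

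*SAP*

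**What the plan says.** The Statistical analysis section of the SAP sets up the primary comparison of DAOH "with encouragement to refer (even/odd birth date) as the binary instrumental variable and treatment setting (NDC v. inpatient) as the exposure". The estimator named is two-stage least squares. On the first stage the plan reads: "In the first stage, we will regress treatment setting on the instrument and all covariates". For the next stage it says that "we will use predicted values of treatment setting to estimate differences in DAOH between arms, adjusting for the same covariates". The adjustment set is given as: "Covariates will include: diagnosis, comorbidity score, age, sex, insurance type, zip code, and race/ ethnicity".

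The second of three secondary analyses is then a "Per-protocol analysis of eligible patients repeating the primary analysis methodology but only among patients who adhered to the assignment and treatment protocol". The SAP does not say what counts as adherence, names no other estimator for this analysis, and plans no correction for selection into the adherent set. Its only inverse-probability weighting is for survey non-response.

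The Sample size and power section assumes that physicians and patients accept "encouragements 50% of the time in the treatment group and there is 10% contamination in the control group". It also states: "In the historical sample, mean DAOH was 26.8 with a SD of 2.2 days".

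**The concern.** An instrumental-variable (IV) analysis tolerates non-adherence because birth date, not the patient's or physician's choice, drives the comparison. That holds only while everyone stays in the analysis. Restricting to adherers selects on something that happened after assignment and that differs by arm: in the even-date arm it keeps those who accepted, in the odd-date arm those who were not referred anyway.

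If adherence is judged by treatment setting in both arms, there is a second consequence. No retained patient has a setting that differs from the assigned arm, so the instrument and the exposure are the same variable and 2SLS has nothing left to correct.

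The result would carry the name of the primary method and a narrower confidence interval than the primary analysis. It could be read as the firmer estimate while lacking the protection that justifies the design.

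**Working it through.** **Inputs (SAP, Sample size and power).** 850 patients, 425 per arm; 50% uptake in the even-date arm; 10% contamination in the odd-date arm; SD of DAOH 2.2 days; two-sided 5% level; 80% power.

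**The plan's own figure.** (1.960 + 0.842) × √(2/425) = 0.192 SD. Dividing by 0.50 − 0.10 = 0.40 gives 0.48 SD, and 0.48 × 2.2 = 1.056 days, which the plan rounds to 1.1. It reproduces.

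**Step 1: the estimator.** Let Z be birth-date arm and D be setting. If every retained patient has D = Z, the first stage fits perfectly with coefficient 1 (0.40 in the full sample). Predicted D equals D, and the second stage is ordinary least squares of DAOH on setting and covariates. In simulated trials the two estimates differed only by rounding error (below 1e-12).

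**Step 2: who remains.** Even-date: 425 × 0.50 = 212.5. Odd-date: 425 × 0.90 = 382.5. Together 595 of 850; 255 (30%) are dropped.

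**Step 3: make-up of the groups.** Assume no defiers. The plan's rates then imply 40% compliers, 10% always-takers (NDC whatever the birth date) and 50% never-takers.
- Retained even-date: 0.40/0.50 = 80% compliers, 0.10/0.50 = 20% always-takers.
- Retained odd-date: 0.40/0.90 = 44% compliers, 0.50/0.90 = 56% never-takers.

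**Step 4: bias.** With no treatment effect, the expected difference is 0.556 × (complier − never-taker DAOH) + 0.20 × (always-taker − complier DAOH), with gaps taken after covariate adjustment. If both gaps equal g, the bias is 0.756g.

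**Step 5: precision.** Adherent set: 2.2 × √(1/212.5 + 1/382.5) = 0.188 day. Primary IV: 2.2 × √(2/425)/0.40 = 0.377 day. The ratio is 2.0.

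**Step 6: size.** The SAP gives no value for g, so the range below is an assumption. Rejection is P(|Z| > 1.96) for a normal variable with mean bias/0.188 and variance 1, when the true effect is zero.

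| Gap g (days) | Bias (days) | Share of 1.056 days | Rejection of a true null |
|---|---|---|---|
| 0 | 0 | 0% | 5% |
| 0.25 | 0.19 | 18% | 17% |
| 0.5 | 0.38 | 36% | 52% |
| 1.0 | 0.76 | 72% | 98% |

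Gaps in the other direction reverse the sign of the bias. A simulation of 3,000 trials per row gave mean estimates of 0.00, 0.19, 0.37 and 0.76 day and rejection of 5%, 18%, 50% and 98%. The full-sample IV stayed within 0.02 day of zero and rejected 5% throughout.

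**Step 7: one-sided exclusions.** Set never-takers at 0, compliers at g and always-takers at 2g; each complete arm then averages 0.40g + 0.10 × 2g = 0.60g.
- Drop only contaminated odd-date patients: (0.60g − 0.444g)/0.50 = 0.31g.
- Drop only even-date decliners: retained even-date patients average 0.80g + 0.20 × 2g = 1.20g, so (1.20g − 0.60g)/(1 − 0.10) = 0.67g.

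In both cases 2SLS does not collapse to ordinary regression, but it is still biased.

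**The case against.** The strongest point is that the collapse depends on a definition the SAP does not give. What is assigned here is an encouragement, which may be declined. Adherence could mean that the encouragement was given or withheld as assigned; 2SLS would then not collapse. The protocol, which is not shown, may define the term. This stands as a condition on the finding, and the missing definition is not in itself the fault. But the text asks for adherence to both the assignment and the treatment protocol, which points to setting, and any two-sided definition by setting gives the result above.

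Second, the bias figures rest on assumed gaps, and equal gaps are at the strong end: in the 1.0-day row, always-takers exceed never-takers by 2.0 days, or 2.0/2.2 = 0.9 SD, after adjustment. If always-takers resemble compliers, the bias is 0.556g. At g = 0.5 that is 0.28 day with 31% rejection, and at g = 0.25 it is 0.14 day with 11%. This is fair; the table is illustrative. The loss of the instrument's protection does not depend on it.

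Third, the 50% and 10% are referral rates, while the exposure is treatment setting. The counts and shares here treat the two as equal, as the SAP does when it scales its IV effect by 0.40.

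Fourth, the analysis is secondary, openly labelled per-protocol, and has no stated precedence. Per-protocol sets generally give up the protection of assignment. That limits the consequence, but it does not justify describing the analysis as a repeat of the IV method.

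Last, the listed covariates and the shared lab and vital limits in the eligibility criteria remove part of the imbalance. They do, but secondary analysis 1 models referral on labs and vitals, and those are absent from the covariates that analysis 2 inherits.

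**Conclusion.** The concern holds. If adherence is judged by setting in both arms, the analysis is covariate-adjusted regression in a post-assignment selection of about 595 of 850 patients. That is algebra and needs no assumption about outcomes. The group shares also assume no defiers and referral equal to treatment setting. The size and direction of bias cannot be read from the SAP: bias is zero with no residual gap, and about 0.28 to 0.38 day for a 0.5-day gap, depending on whether always-takers resemble compliers or exceed them by the same gap. Excluding non-adherers from one arm only also leaves bias.

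The full-sample IV analysis and its power figures are unaffected, and under the no-defiers assumption that analysis already estimates the effect in compliers. This should be fixed before analysis, but it does not threaten the primary result.

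**What to change.** Remove the clause in secondary analysis 2 that carries over the primary method, and state that the full-sample 2SLS already estimates the effect in compliers.

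If a per-protocol estimate is still wanted:
- define adherence for each arm;
- label the analysis exploratory and not an IV analysis;
- weight adherers by the inverse probability of adherence, modelled separately by arm on the primary covariates plus the labs and vitals used in secondary analysis 1.

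Dropping the analysis costs only SAP wording. Keeping it adds one weighting model on data already extracted. The weighted estimate still assumes no unmeasured confounding, and the SAP should say so beside the result.
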